 7. CBC
 8. ESR

9. Levothyroxine dose needed to reach euthyroid state

- Intervention:

The Mediterranean diet MD provides close to 30% energy from total fat (19% from MUFA, 5% from PUFA, 9% from SFA), 15% from protein and 55% energy from carbohydrate (Davis et al., 2015).

The daily caloric requirements of each individual will be set according to the age, and physical activity of the patient as per the tables in the Dietary Guidelines of the Americans, published by the United States Department of Agriculture (USDA, 2015-2020).

Reducing dietary goitrogens will be put into consideration when making meal plans.

At first there will be group sessions of 5-7 patients for 2-3 hours where Mediterranean diet and exchange lists will be explained. Then there will be a one to one (doctor to patient) 1 hour session where the 90 days program will be tailored individually to meet the nutritional requirements, food preferences and socioeconomic status of each patient. The patients will be given handouts displaying the caloric content of foods and the different exchange lists.

For the first four weeks of the program, there will be weekly 2 hour sessions. The first hour will be a group meeting where they can gain support from each other and common concerns can be clarified. Then a 1 hour one to one session will be held.

Adherence of participating cases to the diet regimen will be assessed through the recording in their handouts. Any complaint will be recorded and dealt with and any necessary modifications made.

Pre-intervention clinical and laboratory assessment done at 0 months, will be repeated at 3 months

- Study intervention period: 3 months

- Outcome:

measurement of:

1. Anti-TPO

2. Anti-Thyroglobulin
3. TSH, Free T3, Free T4
4. BMI
5. Lipid profile (Total Cholesterol, HDL, LDL, Triglycerides)
6. Levothyroxine dose needed to reach euthyroid state
7. CBC (to check for adverse events as anemia)

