1. INTRODUCTION/ REVIEW

Hashimoto's thyroiditis (HT) is the most frequent autoimmune thyroid disorder. It is the leading cause of hypothyroidism in the iodine-sufficient areas of the world. Pathogenesis of the disease is thought to be a combination of genetic susceptibility and environmental factors that lead to the loss of immunological tolerance, with a consequent autoimmune attack to the thyroid tissue and appearance of the disease(**Ragusa et al., 2019**). There is growing evidence of the existence of a thyroid–gut axis that controls many autoimmune disorders, and patients frequently report changes in their quality of life and thyroid function as a result of dietary modifications (**Danailova et al., 2022**).

The pathologic features of lymphocytic infiltration, especially of T cells, and follicular destruction are the histological hallmark of autoimmune thyroiditis (AIT), that lead to gradual atrophy and fibrosis. An important role in the immune-pathogenesis ofAITDs is due to inflammatory chemokines and cytokines (**Ragusa et al., 2019**). HT is associated with various thyroid functional states ranging from euthyroid, subclinical to overt hypothyroidism. The most common lab findings demonstrate elevated thyroid-stimulating hormone (TSH) and low

thyroxine (T4) levels, coupled with increased antithyroid peroxidase (anti-TPO) antibodies (**Caturegli et al., 2014**).

Weight gain is frequently the first symptom of hypothyroidism. Research has shown that even when HT patients achieve an euthyroid state, 82% of women treated still have excess body weight, and 35% of them suffer from obesity (**Danailova et al., 2022**). Additionally, euthyroid individuals with HT continue to suffer from symptoms, such as chronic fatigue, dry skin, hair loss, chronic irritability, and nervousness, impairing quality of life (**Ott et al., 2011**).

There is mounting evidence for the existence of a robust thyroid–gut axis. It is reflected by a significant influence of the intrinsic bacterial microflora in the gut on the immune system reactivity and the thyroid function. Dysbiosis may significantly impair the immune system and compromise inflammatory control, causing autoimmune illnesses such as autoimmune thyroid diseases (**Knezevic et al., 2020**). Dysbiosis can also directly affect thyroid hormone levels due to bacterial deiodinase activity and TSH inhibition (**Golan et al., 2013**).

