The premise behind an anti-inflammatory diet as MD is that oxidative stress may be a significant risk factor in the pathogenesis and progression of HT and the development of complications. Therefore, appropriate lifestyle changes should be implemented, including diet and body weight normalization to reduce oxidative stress in these patients. Some vitamins, such as vitamin A, E, or C, and minerals, including Se, which are found in fresh and raw foods, exhibit antioxidant properties. Frequent consumption of these foods reinforces antioxidant defense mechanisms (**Bjørklund & Chirumbolo, 2017**).

For most HT patients, the hormone-replacement therapy with levothyroxine is indispensable. Nevertheless, an appropriate dietary regimen and ecological lifestyle can complement the standard treatment and favor remission of HT by improving the function of the thyroid gland, as well as by regulating the levels of TSH, T3, T4, anti-TPO antibodies. There is still no specific diet recommended for patients with HT, but an anti-inflammatory diet may help HT patients to reduce the need for medicines, slow down the course of the disease, and avoid relapses (**Ihnatowicz et al., 2020**).

Mediterranean diet (MD) is one of the most common anti-inflammatory diets. It is characterized by a large consumption of fruit, vegetables, legumes, nuts, fish, complex carbohydrates, and extra virgin olive oil (EVOO), and a low intake of processed meats, red meats, and sweets. The MD pattern provides a small amount of saturated fatty acid and a high quantity of antioxidants and fiber derived from fruits, vegetables, and EVOO (**Bellastella et al., 2022**). It is conceivable that adoption of this dietary pattern could be protective against HT, counteracting the deleterious effects of oxidative stress and exerting anti-inflammatory and immunomodulatory actions, most likely by affecting cytokine production and gut microbiota composition (**Ruggeri et al., 2021**).

Goitrogens refer to a group of micronutrients that can cause enlargement of the thyroid gland. It includes two main categories which are cruciferous vegetables and soy products. Goitrogens have been shown to inhibit thyroid hormones synthesis in several ways, mostly by inhibiting iodine utilization. Those micronutrients have to be taken in consideration specially in those with thyroid diseases or who are iodine deficient (**Babiker et al., 2020**).

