2. AIM/ OBJECTIVES

This study aims to assess the impact of Mediterranean diet on patients with Hashimoto thyroiditis using the following outcomes:

Primary outcomes: Anti-TPO antibodies, Anti-Thyroglobulin antibodies, TSH, T3, T4

Secondary outcomes: BMI, Lipid profile, Symptoms of hypothyroidism

3. METHODOLOGY:

Patients and Methods/ Subjects and Methods/ Material and Methods

- All participants will be subjected to an interview questionnaire including data pertaining name, age, sex, occupation, past medical history, 24 hours dietary recall, general clinical examination, anthropometric measures of weight, height, BMI, and biochemical Investigations including Lipid profile (Cholesterol/HDL ratio, triglycerides), HbA1C, TSH, free T3, free T4, Anti-TPO, Anti-Thyroglobulin.
- **Type of Study:** single-arm open label clinical trial
- **Study Setting:** Outpatient clinics of Ain Shams University hospitals, Cairo, Egypt.
- **Study Population:** this study will be conducted on patients with HT
- **Inclusion Criteria:**
 1. - Female and male patients with HT diagnosed by a combination of clinical features of hypothyroidism and presence of anti-thyroid antibodies.
 2. - Age from 20 to 50 years old
- **Exclusion Criteria:**
 1. -Pregnant or lactating females
 2. -Age below 20 years and above 50 years
 3. -presence of any other medical disorder
- **Pre-intervention Baseline assessment:**
 1. Anti-TPO
 2. Anti-Thyroglobulin
 3. TSH, free T3, free T4
 4. BMI (measured in kg/m²)
 5. Lipid profile (Total Cholesterol, HDL, LDL, Triglycerides)
 6. HBA1C, Fasting Blood Sugar, 2 hours Post Prandial

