8. ESR

- **Sample Size:** Using the G power program for sample size calculation, setting power at 80% alpha error at 5%, reviewing results from previous studies (Danailova et al, 2022, and Bellastella et al, 2022) showed that HT patients showed a high intake of animal proteins, saturated fats, and refined sugar-in other words, the prototype of the so-called Western-type diet, in contrast with the Mediterranean one. Also, intake of the Mediterranean diet is associated with improving symptoms, assuming an effect size difference =0.5 regarding AB levels before and after dietary intervention and after a 10% adjustment for dropout rate, a sample size of at least 40 patients will be needed.
- **Sampling Method:** Convenience sampling such as that all male and female patients with HT will be invited to join the Mediterranean Diet regimen. Those who agree to participate and provide a written informed consent will be enrolled in the study.
- **Adverse events:** Possible adverse events in terms of anemia or disturbance of lipid profile will be assessed at 3 months and the patient withdrawn from the study if they occur.
- **Ethical Considerations:** A written informed consent will be obtained from each patient before enrolment in this study.

Statistical Analysis: Data will be collected and entered into the software and edited for errors. Data were expressed as median and interquartile range. Analytical statistics were done using the Wilcoxon rank test and Spearman correlation test. The Wilcoxon rank test was used to compare parameters expressed in median and IQR pre- and post-intervention. The Spearman

correlation test was used to measure the direction and strength of association between different study parameters. The P-value was used to measure the level of significance, where $P > 0.05$: non-significant (NS), $P < 0.05$: significant (S), and $P < 0.01$: highly significant (HS).

- **software to be used:** SPSS (Statistical Package for Social Sciences) version 20 will be the statistics software to be used. Citation of SPSS: IBM Corp. Released 2011. IBM SPSS Statistics for Windows, Version 20.0. Armonk, NY: IBM Corp.

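### Minor: the levothyroxine dose needed on the diet is unconfirmed for patients out of range at month 3, and an all-patient pre/post comparison can pick up ordinary dose correction

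*Combined protocol and SAP*

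**What the plan says.** All references are to the combined protocol and SAP.

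- **Dose item.** Section 3 (Methodology) lists "Levothyroxine dose needed to reach euthyroid state" as item 9 of the baseline assessment and, in the same words, as item 6 of the outcomes. It does not say whether this is the dose being taken or the dose set at the visit. It does not define euthyroid and gives no titration rule.
- **Timing.** Section 3, Intervention: "Pre-intervention clinical and laboratory assessment done at 0 months, will be repeated at 3 months". The weekly sessions of the first four weeks list no laboratory test, and nothing is planned after month 3.
- **Entry.** Section 3, Inclusion Criteria: patients aged 20 to 50 with HT "diagnosed by a combination of clinical features of hypothyroidism and presence of anti-thyroid antibodies". Under Sampling Method, "all male and female patients with HT will be invited to join the Mediterranean Diet regimen". No criterion concerns current TSH or time on a fixed dose. Section 1 notes that "HT is associated with various thyroid functional states ranging from euthyroid, subclinical to overt hypothyroidism".
- **Design and analysis.** The trial is single-arm and open label. Statistical Analysis compares parameters before and after with a Wilcoxon test. It names no subset and does not mention dose.
- **Standing of the item.** Section 2 gives antibodies, TSH, T3 and T4 as primary, then "Secondary outcomes: BMI, Lipid profile, Symptoms of hypothyroidism". Dose is in neither tier.
- **Why dose is of interest.** Section 1 says "For most HT patients, the hormone-replacement therapy with levothyroxine is indispensable" and that "an anti-inflammatory diet may help HT patients to reduce the need for medicines".

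**The concern.** A needed dose is known only once TSH has been seen in range on the dose being taken. With two tests, that can be shown on the diet only at month 3, and only for patients who are in range then.

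The second difficulty is the comparison. Patients may enter over-dosed, under-dosed or untreated, and the 0-month TSH gives their physician a reason to adjust. Without a control arm, nothing shows what that adjustment would have done alone. Correcting over-dosed patients could be read as the reduced need for medicines that Section 1 anticipates. Correcting under-dosed patients could be read as harm, or could hide a real saving in dose.

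The consequence reaches beyond the dose item. A dose changed after month 0 also shifts the month-3 TSH, free T3 and free T4, so the primary thyroid results carry the same ambiguity in those patients.

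**Working it through.** **1. The plan's own figure.** The stated sample size is at least 40, from effect size 0.5 on antibody levels, 80% power, 5% alpha and 10% dropout. A two-sided paired t test needs 34, and 34/0.9 = 37.8, so 38. The Wilcoxon version (normal data, efficiency 3/π) needs 35, and 35/0.9 = 38.9, so 39. Both are within two of 40, so the figure is not in dispute. It does not depend on dose. Completers: 40 × 0.9 = 36.

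**2. What each reading of the item can show.**
- *Dose being taken.* Among scheduled tests, only the pre-diet TSH can have guided a change visible at month 3. A change in need caused by the diet would show in the month-3 TSH, not in the dose.
- *Dose set on that visit's result.* The month-3 value reflects the diet but is untested if it is a change. If correction takes more than one step, later steps still fall between the two values.
- *Dose already titrated to euthyroid before baseline.* The problem largely disappears, but the plan does not require this.

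**3. Illustration under the dose-taken reading.** The document gives neither the number on levothyroxine nor the share mis-dosed, so every share here is an assumption. Also assumed: no diet effect, each mis-dosed patient corrected once after month 0, and changes of equal size.

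With zeros dropped and equal-size changes, the signed-rank test reduces to a sign test. For u increases and d decreases, m = u + d:
- exact two-sided P = 2 × Pr[Bin(m, ½) ≤ min(u, d)];
- normal approximation z = |u − d|/√m.

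For example, 4 v 0 gives exact 2 × 0.5⁴ = 0.125, but z = 4/2 = 2 and P = 0.0455. 6 v 0 gives exact 2 × 0.5⁶ = 0.031.

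For n treated completers with shares a and b mis-dosed in the two directions, the chance of P < 0.05 is the sum of n!/(u! d! (n−u−d)!) × aᵘ bᵈ (1−a−b)ⁿ⁻ᵘ⁻ᵈ over all significant (u, d). Cells are exact / approximate, in %:

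| Mis-dosed one way v other | n = 36 | n = 25 | n = 18 |
|---|---|---|---|
| 5% v 0 | 0.8 / 10 | 0.1 / 3 | <0.1 / 1 |
| 10% v 0 | 15 / 49 | 3 / 24 | 0.6 / 10 |
| 10% v 5% | 3.6 / 11 | 1.3 / 8 | 0.3 / 5 |
| 20% v 0 | 75 / 95 | 38 / 77 | 13 / 50 |
| 20% v 5% | 31 / 43 | 17 / 31 | 7 / 24 |
| 20% v 10% | 12 / 17 | 7 / 13 | 4 / 11 |
| 20% v 20% | 2.7 / 4.7 | 2.2 / 4.2 | 1.7 / 4.5 |

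The plan does not say which version of the test will be run. No rate can be given for the dose-set reading, because there is no titration rule to model.

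**4. What a restricted comparison could do.** If 20, 40 or 60% of 36 treated completers are out of range at month 0, the subset is 36 × 0.8, 0.6 or 0.4 = 28.8, 21.6 or 14.4, so about 29, 22 or 14. The same formula gives (exact / approximate, %):

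| Assumed at month 3 | n = 29 | n = 22 | n = 14 |
|---|---|---|---|
| 30% set lower, 5% higher (power) | 55 / 66 | 38 / 53 | 14 / 37 |
| No diet effect, 10% v 0 drift | 6 / 33 | 2 / 17 | 0.2 / 4 |
| No diet effect, 20% v 0 drift | 54 / 86 | 27 / 67 | 4 / 30 |

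Restriction removes correction of baseline mis-dosing but not later drift out of range. A stable-dose rule would shrink the subset further.

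**The case against.** The strongest reply is that the item names the dose needed, and for a mis-dosed patient the dose taken on arrival is by definition not that dose. The wording thus supports the dose-taken reading least, yet every mis-dosing rate above rests on it. This stands: the rates are an illustration under one reading. It does not rescue the item, because naming the target supplies no way to establish it at either visit.

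It is also fair that harm needs several conditions the document does not state: mis-dosing mostly one way, correction during the study, dose actually tested, and the result then read causally. Any before-after change in a single-arm trial is also hard to attribute to the diet. That limits the point to a minor one. It goes further than a missing definition, however, since a definition alone would leave an all-patient comparison mixed with titration.

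A reader might infer more than the document supports:
- *That the dose result will be a false finding.* The baseline mix is unknown, and Statistical Analysis does not name dose for testing.
- *That the risk matters only above some share mis-dosed, such as 10%.* Any such threshold depends on the test: 5% v 0 at n = 36 gives 0.8% exact but 10% by approximation.
- *That the risk is confined to the dose item.* TSH, T3 and T4 are primary and respond to dose.
- *That the bias must favour the diet.* The document does not give the direction of mis-dosing. The diagnostic criterion describes how HT was identified, not current control.

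**Conclusion.** The point holds as a minor one, worth acting on because the remedy is cheap. As planned, the dose needed on the diet is confirmed only for patients in range at month 3 on the dose they are taking. A pre/post dose test in all patients could reflect correction of baseline mis-dosing, upward or downward, and dose changes during the study also blur the primary thyroid hormone results.

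The size is not determinable from the document. It depends on how the item is read, how one-sided the mis-dosing is, how many patients are treated, and which version of the Wilcoxon test is run. In the central example the false-positive rate is about 31% to 43%; with balanced mis-dosing it does not exceed 5%. The sample size and antibody calculation are unaffected.

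**What to change.** For patients on levothyroxine:

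1. At each visit record the dose being taken, how long it has been taken, any change since the last visit with its reason, and the dose set on that visit's result. State the TSH range that counts as euthyroid.
2. Make the month-3 decision (lower, unchanged, higher), as counts beside the same-visit TSH, the main dose result. State that a dose changed at month 3 is not confirmed by a later test.
3. Limit any pre/post dose comparison to patients in range at month 0 on a dose unchanged for a stated minimum period. Name the version of the Wilcoxon test.
4. Add a sensitivity analysis of TSH, free T3 and free T4 in patients whose dose did not change between 0 and 3 months.
5. Describe the others separately, including anyone who starts treatment during the study, and make no diet claim from their dose change.

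If patients are in fact titrated to euthyroid before baseline, saying so in the Inclusion Criteria would settle the baseline part.

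The cost is a few extra entries per visit, one subset, one sensitivity analysis and a caveat. No extra visit, test or patient is needed. The drawback is a small, weak subset still open to drift. If the normal approximation is used, its false-positive rate is well above the exact-test figure, which is why the counts should lead.

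### Anaemia and lipid disturbance are assessed patient by patient at 3 months, but the plan has no count of cases, no baseline rule and no statement on whether withdrawn cases stay in the pre/post analysis

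*Combined protocol and SAP*

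**What the plan says.** All references are to the Methodology section of the combined protocol and SAP.

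- **Outcome list:** the blood count is included as "CBC (to check for adverse events as anemia", closing the bracket.
- **Adverse events:** "Possible adverse events in terms of anemia or disturbance of lipid profile will be assessed at 3 months". The same item then sets a consequence for anyone affected: "the patient withdrawn from the study if they occur".
- **Intervention (timing):** "Pre-intervention clinical and laboratory assessment done at 0 months, will be repeated at 3 months". The baseline list includes both the blood count and the lipid profile, so each patient should have a before and an after value.
- **Statistical Analysis:** "Data were expressed as median and interquartile range". For methods, "Analytical statistics were done using the Wilcoxon rank test and Spearman correlation test". For the pre/post comparison, "The Wilcoxon rank test was used to compare parameters expressed in median and IQR pre- and post-intervention". A P value above 0.05 is labelled non-significant.

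The document does not define anaemia or lipid disturbance. It plans no count, proportion, confidence interval or shift table for either, and does not say how a case already present at baseline is treated. It also does not say whether a patient withdrawn for an event contributes to the pre/post analysis.

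**The concern.** Checking for anaemia as an adverse event asks how many patients became anaemic. A median with a Wilcoxon test asks whether the group as a whole shifted. The two questions part company when harm falls on a few patients: the median barely moves and the test has little power.

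The withdrawal sentence adds a second problem. It acts at 3 months, which is also the end of the intervention and the only follow-up assessment. If withdrawn patients are then left out of the pre/post comparison, which the plan does not rule out, the affected patients are exactly the ones removed from the only comparison planned.

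At stake is the estimate of the only two harms that the protocol names. A non-significant blood-count result could be read as reassurance when several patients were affected.

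**Working it through.** **1. The plan's own number.** Inputs from Sample Size: effect size 0.5, power 80%, alpha 5% (sidedness not stated; two-sided assumed), 10% dropout.

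- Paired t test by noncentral t: n = 34; 34 / 0.9 = 37.8, so 38.
- Wilcoxon signed-rank with efficiency 3/π: n = 35; 35 / 0.9 = 38.9, so 39.

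Both agree with at least 40, so the sample size is not in dispute. It was set on antibody levels, not on the blood count. Expected completers: 40 × 0.9 = 36.

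**2. What the planned test would show.** The documents give no haemoglobin figures, so these are assumptions: mean 13 g/dL, between-patient SD 0.9, visit-to-visit SD 0.3-0.5. Affected patients fall by 1.5-2 g/dL and the rest have no true change. The Wilcoxon test is read as the paired signed-rank test, two-sided at 5%, with n = 36 and at least 2,000 simulated trials per scenario.

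| Affected patients | P < 0.05 if retained | P < 0.05 if left out |
|---|---|---|
| 3 of 36 | about 9-11% | about 5% |
| 4 of 36 | about 12-16% | about 5% |
| 6 of 36 | about 24-31% | about 5% |

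With 4 affected, the group median moves by only about 0.13-0.15 g/dL. A second set of assumptions (fall of 2 g/dL, SD of change 0.5-0.8) gives 14-15% for 4 of 36 and 26-31% for 6 of 36. With affected patients left out, the simulated rates stay between 4% and 6% however many were affected, which is the test's false-positive rate.

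**3. What a count would show.** Exact (Clopper-Pearson) 95% intervals need no haemoglobin assumption.

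- 0/36: the upper limit solves (1 − p)^36 = 0.025, so p = 1 − 0.025^(1/36) = 9.7%.
- 4/36 = 11.1%: interval 3.1% to 26.1%.
- If all 40 have a 3-month sample, 0/40: 1 − 0.025^(1/40) = 8.8%.

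**4. Why the baseline value matters.** Take an assumed limit of 12 g/dL, for illustration only, with mean 13.0-13.3 and the SDs above. With no true change in anyone, 3-8% of patients at or above the limit at baseline fall below it at 3 months. If all 36 started at or above it, that is 36 × 0.03 = 1.1 to 36 × 0.08 = 2.9 patients. A bare count therefore includes some chance crossings. Crossings in the other direction indicate how large that component is, so both directions are needed.

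**The case against.** The strongest reply is that the plan already finds cases individually: nobody can be withdrawn for anaemia without being identified. That stands. A reader might infer that the trial will report no safety signal, or will declare the diet safe on a non-significant P value. The documents do not support this. They nowhere say that safety will be judged from the Wilcoxon test, and the investigators may list cases unprompted. False reassurance is a possible result, not one that the plan dictates. But identifying a case is not the same as planning to report it with a definition and a denominator.

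A reader might also infer that pre-existing anaemia will be charged to the diet. That goes too far. The Exclusion Criteria remove patients with any other medical disorder, which may exclude some anaemic patients, and the adverse-event wording can be read as new onset. The gap that remains is that anaemia is not named as an exclusion, no limit is given, and the blood count is listed as a baseline assessment, not as a screening test.

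Third, the 12-16% figure assumes that affected patients are retained. That is correct, and it is why both cases are shown; leaving them out makes detection worse.

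Finally, the haemoglobin inputs come from outside the documents, and the objectives list no safety aim. Both are true. They limit the precision and weight of the point, but not the mismatch between the stated purpose of the blood count and its only stated summary.

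**Conclusion.** The concern holds in this limited form. The protocol names two harms and assesses them per patient, yet its only stated summary is a comparison of group medians, which is unfit for detecting harm in a minority. Under the stated assumptions, 4 of 36 affected patients would produce a significant result in about 12-16% of trials if retained and about 5% if left out. The exact percentages depend on the assumed haemoglobin values, but two sets of assumptions give similar results.

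It would be too strong to say that the safety conclusion will be wrong, because the plan states no safety conclusion and no rule for reaching one. The efficacy analyses' stated methods, the data collection and the sample size of 40 are not challenged here.

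**What to change.** In Statistical Analysis:

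1. State the definitions of anaemia and lipid disturbance in advance. The limits are for the sponsor to choose.
2. Report new anaemia and new lipid disturbance, meaning absent at baseline and present at 3 months, as n/N with exact 95% confidence intervals.
3. Add a baseline-by-3-month shift table for each, showing normal to abnormal and abnormal to normal.
4. Include every patient with a 3-month sample, including those withdrawn for the event.
5. Reconcile the withdrawal sentence with the pre/post analysis by stating whether withdrawn patients' 3-month values are used. This concerns the use of data only; the clinical rule is not addressed here.
6. Call these events treatment-emergent without attributing them to the diet, since a single-arm study cannot separate a diet effect from chance crossing or other causes.
7. Base no safety statement on the Wilcoxon P value.

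**Cost:** a few sentences and one extra table from data already collected, with no new tests and no change in sample size. The drawback is presentational: with no cases, an upper limit of about 10% (9.7% for 0/36) is less reassuring than a non-significant label, but it shows what a study of this size can exclude.
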